
Geometric mean ratio calculated at Day 22/Day 1.Percentage of subjects with an HI titer $\geq 1:40$.¹Percentage of subjects achieving seroconversion (defined as: HI titer $\geq 1:40$ for subjects sero-negative at baseline [HI titer $< 1:10$]; or a minimum 4-fold increase in HI titer for subjects sero-positive at baseline [HI titer $\geq 1:10$]) on Day 22.¹Reverse cumulative distributions of HI titers at Day 22. 
Exploratory Endpoint(s):
 
The exploratory endpoints determined by the microneutralization (MN) assay against homologous strains at Days 1 and 22, include the following:
 
Geometric mean titer (GMT).Geometric mean ratio calculated at Day 22/Day 1.Percentage of subjects with a four-fold rise in MN antibody titer at Day 22Reverse cumulative distributions of MN titers at Day 22. 
Additionally, an estimate of the serologic correlate of protection on the basis of HI or other immunological responses including MN, measured three weeks after vaccination against the respective strain
		

¹ The endpoints based on percent of subjects achieving seroconversion and HI titer $\geq 1:40$ at Day 22 will be assessed against the criteria described in CBER Guidance Clinical Data Needed to Support the Licensure of Seasonal Inactivated Influenza Vaccines (2007). Specifically, this will be that:

- The lower bound of the two-sided 95% CI for the percent of subjects achieving seroconversion for HI antibody should meet or exceed 30%
- The lower bound of the two-sided 95% CI for the percent of subjects achieving an HI antibody titer $\geq 1:40$ should meet or exceed 60%

Name of Sponsor: Seqirus UK Ltd.	Protocol number: V118_18	Generic name of study vaccine(s): MF59-adjuvanted Quadrivalent Subunit Inactivated Egg-derived Influenza Vaccine Tetanus Toxoid, Reduced Diphtheria Toxoid and Acellular Pertussis Vaccine, Adsorbed
Statistical Analyses:		
Criteria for Assessing Primary Efficacy Objective:		
Primary Efficacy Objective:		
The primary measure of absolute efficacy will be tested in elderly subjects ≥ 65 years of age according to the following null (H_0) and alternative (H_1) hypotheses:		
$H_0: 1 - HR = VE \leq 0.4$ versus $H_1: VE > 0.4$		

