For the first secondary efficacy objective: With group vaccine efficacy of 65% but expecting conservatively reduced ERs of RT-PCR confirmed influenza cases due to matched strains of 2.5% among subjects in the non-influenza comparator group and 0.9% among the aQIV group then 144 events are estimated with power approximately 88.5% to show the absolute efficacy of aQIV versus non-influenza comparator, using a margin of 40% for lower bound of the 95% CI.		
Assuming a drop-out rate of 10%, approximately 10,692 subjects \geq 65 years, 5,346 per vaccine group will be randomized to receive either aQIV or non-influenza comparator (Boostrix®) in a 1:1 allocation ratio, stratifying by age groups: \geq 65 to 74 and \geq 75 years of age and by the presence or absence of medical co-morbidity (see Section 5.1.2, Screening for assessment of comorbidity and risk of complications)		

² The attack rate of 3.5% is estimated based on the attack rate published in placebo controlled studies (DeVilliers, 2009; Treanor, 2011; Frey, 2009)

Name of Sponsor: Seqirus UK Ltd.	Protocol number: V118_18	Generic name of study vaccine(s): MF59-adjuvanted Quadrivalent Subunit Inactivated Egg-derived Influenza Vaccine Tetanus Toxoid, Reduced Diphtheria Toxoid and Acellular Pertussis Vaccine, Adsorbed
--	------------------------------------	---

from influenza).

Sample Size for Secondary Immunogenicity Objective (Immunogenicity Subset):

The immunogenicity objective is considered as secondary and so no alpha adjustment for multiplicity will be done for the analysis therefore a significance level of 5% (2-sided) or 2.5% (1-sided) was used for sample size calculation.

Using the following assumptions from the V70_27 study in elderly adult subjects: specifically after aTIV vaccination, seroconversion rates, H1N1: 77%, H3N2: 74% and B: 47%, and percentages of subjects with a HI titer ≥ 40 , H1N1: 91%, H3N2: 99%, B: 64% (Table 1).

With samples analyzed from 1,362 subjects (1,226 evaluable subjects assuming a rate of 10% for missing data) in the aQIV group there will be at least 80% power to evaluate CBER criteria with all four strains contained in aQIV.

Table 1: CBER criteria for subjects ≥ 65 years of age

Strain	π_i (proportion in aQIV, based on data of V70_27)	π_0 (CBER threshold)	Sample size for aQIV	Marginal Power
Proportion of subjects with Seroconversion				
H1N1	77%	30%	1226	99%
H3N2	74%	30%	1226	99%
B strains	47%	30%	1226	99%
Proportion of subjects with HI titer ≥ 40				

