4. RANDOMIZATION AND BLINDING

4.1 Method of Group Assignment and Randomization

Approximately 10,620 subjects ≥ 65 years will be randomized to receive either aQIV or non-influenza comparator in a 1:1 allocation ratio, stratifying according to age (≥ 65 to 74 and ≥ 75 years), study site and comorbidity status (at risk/not at risk). Each randomized subject will be automatically assigned a unique Subject identification (ID) and Pack ID indicating the assigned treatment. The Subject ID will be the subject's unique identification number for all CRFs and associated study documentation that will be used for duration of the study.

The Subject ID consists of a 7-digit number resulting from the combination of the site number, and the subject's order of randomization at the site. After randomization, the Screening Number ceases to be used and remains in the Screening and Enrolment Log only. The list of randomization assignments is produced by the Interactive Response Technology (IRT) service provider and approved by Seqirus or delegate.

One season in which at least 2800 subjects are anticipated to be enrolled will be selected for the collection of immunogenicity samples. Samples from first 2800 subjects participating in the selected season (1,400 from each treatment arm) will be collected at Day 1 (baseline) and Day 22 (Visit 3). In order to maintain the study blind equal numbers of subjects from both treatment groups will be asked to provide blood specimens. After all of the specimens have been obtained, a subset of subjects with both samples collected will be randomly selected on a 4:1 ratio (1,362 aQIV; 340 Boostrix) for the purpose of completing the analysis of the immunogenicity objectives. The selected subjects will constitute the Immunogenicity Set. The samples from the selected subjects will be randomized into batches for HI testing in such a way that both samples from one subject are contained within one batch, but the sequence of samples is random. See [section 4.2](#) for discussion of maintaining the study blind with respect to the selected Immunogenicity Set subjects. Serum samples from subjects with RT-PCR confirmed influenza, along with a subset of subjects who did not have RT-PCR confirmed influenza, may be tested to estimate the correlate of protection. The serologic component of the correlate of protection will be measured using either a validated haemagglutination inhibition (HI) and/or other immunological assays (such as microneutralization).

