Anti-HA antibody will be measured using a validated haemagglutination inhibition (HI) assay with egg-derived HA antigens from homologous strains of the virus.

The immunogenicity objective is considered as secondary and so no alpha adjustment for multiplicity will be done for the analysis therefore a significance level of 5% (2-sided) or 2.5% (1-sided) was used for sample size calculation. One season in which at least 2800 subjects are anticipated to be enrolled will be selected for the collection of immunogenicity samples. Samples from approximately 2800 subjects participating in the immunogenicity season will be obtained. In order to maintain the study blind blood samples from an equal number of subjects participating in both treatment groups will be collected at Day 1 (baseline) and Day 22 (visit 3).

After all of the specimens have been obtained a subset of samples from those collected will be randomly selected on a 4:1 ratio for analysis. In total approximately 1,702 samples are planned to be included the analysis (1,362 aQIV; 340 Boostrix). The details and the guidelines regarding the selection process of these samples can be found in the SAP.

Following assumptions from the V70_27 study in elderly adult subjects were used: specifically after aTIV vaccination, seroconversion rates, H1N1: 77%, H3N2: 74% and B: 47%, and percentages of subjects with a HI titer ≥ 40 , H1N1: 91%, H3N2: 99%, B: 64%.

With samples from at least 1,362 enrolled subjects (1,226 evaluable subjects assuming a rate of 10% for missing data in the aQIV group) there will be enough power to evaluate achievement of CBER criteria with all four strains contained in the vaccine (see [Table 5-1](#)).

Table 5-1: Power to assess CBER criteria for subjects ≥ 65 years of age

Strain	π_i (proportion in aQIV, based on data of V70_27)	π_0 (CBER threshold)	Sample size for aQIV	Marginal Power
Proportion of subjects with Seroconversion				
H1N1	77%	30%	1226	99%
H3N2	74%	30%	1226	99%
B strains	47%	30%	1226	99%
Proportion of subjects with HI titer $\geq 1:40$				
H1N1	91%	60%	1226	99%
H3N2	99%	60%	1226	99%
B strains	64%	60%	1226	82%

Safety objectives:

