11. IMMUNOGENICITY ANALYSIS

Where applicable, immunogenicity objectives will be evaluated using Center for Biologics Evaluation and Research (CBER) Guidance Clinical Data Needed to Support the Licensure of Seasonal Inactivated Influenza Vaccines (CBER 2007).

For the elderly population the CBER criteria are as follows:

- the lower bound of the two-sided 95% confidence interval (CI) for the percent of subjects achieving seroconversion for HI antibody should meet or exceed 30%
- the lower bound of the two-sided 95% CI for the percent of subjects achieving an HI antibody titer $\geq 1:40$ should meet or exceed 60%.

Both endpoints should be met for each strain included in the vaccine.

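### The synopsis claim of at least 80% power for the CBER criteria in all four strains rests on the power for one B strain; the chance that both B strains pass is about 67% if independent and at most 82%

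*Protocol*

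**What the plan says.** The protocol synopsis, under the sample size for the secondary immunogenicity objective, states that with 1,362 aQIV subjects analysed, of whom 1,226 are evaluable after 10% missing data, "there will be at least 80% power to evaluate CBER criteria with all four strains contained in aQIV". Table 1 beneath it has one row for the B strains under each criterion, and its last column is headed marginal power. The lowest entry is 82%, for the B strains on HI titre of at least 1:40. All other entries are 99%.

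Protocol 8.5 and SAP section 5 repeat the table but make a weaker claim; in SAP section 5 it reads "there will be enough power to evaluate achievement of CBER criteria", again with reference to all four strains. Neither document gives a joint power or a correlation between strains.

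SAP section 11 sets the success rule for the CBER criteria: "Both endpoints should be met for each strain included in the vaccine". The vaccine contains A/H1N1, A/H3N2, B/Yamagata and B/Victoria.

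On the samples, SAP 4.1 collects blood from 1,400 subjects per arm, after which "a subset of subjects with both samples collected will be randomly selected on a 4:1 ratio", giving 1,362 aQIV and 340 Boostrix subjects.

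**The concern.** An all-strain success rule is a joint event over eight tests: four strains by two criteria. Its probability cannot exceed that of the weakest test, and it is lower when two weak tests do not always succeed or fail together. Here the weakest test, at 82%, occurs twice, once for each B lineage. Carrying the 82% into a sentence about all four strains treats the two B strains as one.

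What is at stake is the stated chance of meeting a formal secondary criterion. On the synopsis sentence, a reader would put the risk of failing it at no more than 1 in 5. Under the plan's own response rates it could be as high as 1 in 3, depending on a correlation that is not stated.

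**Working it through.** **Inputs from the documents**
- Level: "a significance level of 5% (2-sided) or 2.5% (1-sided) was used for sample size calculation" (synopsis; also Protocol 8.5 and SAP section 5), with no multiplicity adjustment.
- Assumed seroconversion: "H1N1: 77%, H3N2: 74% and B: 47"%. Assumed proportion with HI titre of at least 1:40: "H1N1: 91%, H3N2: 99%, B: 64"%. The single B figure is applied to both B strains.
- Thresholds: the lower 95% limit for "subjects achieving seroconversion for HI antibody should meet or exceed 30"%; for the titre criterion the threshold is 60%.
- Interval: Clopper-Pearson (Protocol 8.4.3.3.3, SAP 11.3).
- Evaluable aQIV subjects: 1,362 × 0.9 = 1,225.8, i.e. 1,226.

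**Input not in the documents**
- The correlation ρ between the two B-strain test results. I assume ρ ≥ 0 and show the range.

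**1. Reproduce the plan's figure for one B strain.** The smallest count whose lower Clopper-Pearson limit reaches 0.60 is 770 of 1,226. Exact power is P(X ≥ 770 | n = 1,226, p = 0.64) = 81.6%. The normal approximation (score test) gives Φ{[0.04 − 1.96·√(0.60·0.40/1,226)] / √(0.64·0.36/1,226)} = Φ{(0.0400 − 0.0274)/0.0137} = 82.1%. The stated 82% is correct as the power for one strain.

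**2. The other tests.** Each of the six remaining strain-by-criterion tests has power of about 100% at n = 1,226. Power for all eight is therefore, to the accuracy needed, the chance that both B strains meet the titre criterion.

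**3. Joint power.** With equal marginal power P and z = Φ⁻¹(P), joint power is the bivariate normal probability Φ₂(z, z; ρ).

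| ρ (assumed) | P = 81.6% (exact) | P = 82% (as stated) |
|---|---|---|
| 0 | 66.6% | 67.2% |
| 0.5 | 71.0% | 71.5% |
| 0.8 | 74.9% | 75.4% |
| 0.9 | 76.9% | 77.3% |
| 0.99 | 80.1% | 80.5% |
| 1 | 81.6% | 82% |

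The first row is simply 0.816² or 0.82². If negative correlation were allowed, the floor would be 2 × 0.816 − 1 = 63%.

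**4. Size needed for 80% jointly.** Under independence each B strain needs √0.80 = 89.4% power, which takes about 1,560 evaluable aQIV subjects. That is more than the 1,400 to be bled.

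**5. Sample counts.** SAP 4.1 draws the 1,362 from subjects who already have both samples, yet the power text takes a further 10% off them. Drawing 1,362 from 1,400 tolerates a loss of (1,400 − 1,362)/1,400 = 38/1,400 = 2.7% of pairs. The possibilities are:
- 10% lost before selection only: 1,400 × 0.9 = 1,260 pairs, fewer than 1,362 but more than 1,226; power per B strain is 82.5%.
- 10% lost after selection only: 1,226, as the plan states.
- 10% lost at both steps: 1,260 × 0.9 = 1,134; power per B strain is 77.6%.

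**The case against.** The best defence is that nothing is hidden. The table directly below the sentence labels its column as marginal power. The hypotheses are indexed by strain and tested at an unadjusted level, and Protocol 8.2.2.3 does not state an all-strain rule. The sentence can be read as at least 80% for each of the four strains, which is true. It appears only in the synopsis; Protocol 8.5 and SAP section 5 claim no percentage in the text. The objective is secondary, and study success turns on primary efficacy, together in Protocol 8.2 with an acceptable safety profile.

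Much of this stands. The table is right, no calculation in it is wrong, and no trial decision depends on the sentence. It does not rescue the sentence, which speaks of the criteria with all four strains, while SAP section 11 makes success depend on every strain. A reader who combines the two will take 80% as the chance of meeting the rule.

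Two stronger readings are tempting and are not supported.
- A reader might take joint power to be 67% to 77%. The upper end only reflects stopping at a correlation of 0.9. The documents give no correlation, so the range for non-negative values runs up to 82%.
- A reader might conclude that 1,362 sample pairs are out of reach under the plan's own 10% loss. The plan applies that 10% to the 1,362, not to the 1,400 bled, and gives no rate for loss of pairs. Even 1,260 pairs would exceed the 1,226 on which the stated power rests.

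**Conclusion.** Wrong as written. The 82% is sound as the power for one B strain; the synopsis extends it to all four strains, where it does not apply. At 1,226 evaluable subjects and the plan's response rates, joint power is about 67% if the two B-strain results are independent, 71% at correlation 0.5, 77% at 0.9 and at most 82% with perfect correlation. It reaches 80% only at a correlation of about 0.99. This rests on an assumed non-negative correlation, a bivariate normal approximation for the pair of results, and the plan's use of 64% for both B strains.

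The 10% missing rate is a lesser point, an inconsistency only: it is taken off a set already defined as having both samples. By itself this does not lower the stated power. Power per B strain falls below 80%, to 77.6%, only if 10% is lost both before and after selection.

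**What to change.** In the synopsis, and for clarity in Protocol 8.5 and SAP section 5, replace the power statement with wording such as: *about 82% for each B strain on the HI titre criterion; joint power for all four strains about 67% if the two B-strain results are independent, rising to at most 82% with perfect correlation (correlation assumed, 1,226 evaluable aQIV subjects).*

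In SAP 4.1, state whether the 10% applies before or after selection, and define the aQIV set as all aQIV subjects with both samples, up to 1,362. Carry the same definition into the immunogenicity full analysis set in Protocol 8.3.4 and SAP 7.3, which now fix the total at 1,702. If losses are expected at both steps, base the stated power on the resulting number.

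The cost is text only. No test, threshold or sample size changes, but the stated power becomes less favourable.

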AESI	Adverse Events of Special Interest
BLA	Biologics Licensure Application
B&SR	Biostatistics and Statistical Reporting
BMI	Body Mass Index
CBER	Center for Biologics Evaluation and Research
CDC	Centers for Disease Control and Prevention
CHMP	Committee for Medicinal Products for Human Use
CI	Confidence Interval
CRF	Case Report Form
CRO	Contract Research Organization
CSR	Clinical Study Report
DCF	Data Clarification Form
DMC	Data Monitoring Committee
EC	Ethics Committee
eCRF	Electronic Case Report Form
EDC	Electronic Data Capture
EMA	European Medicines Agency
ER	Event Rate
FAS	Full Analysis Set
FDA	United States Food and Drug Administration
GCP	Good Clinical Practices
GMC	Geometric Mean Concentration
GMR	Geometric Mean Ratio
GMT	Geometric Mean Titer
HA	Haemagglutinin
HI	Haemagglutination Inhibition
HIPAA	Health Insurance Portability and Accountability Act
HIV	Human Immunodeficiency Virus
IB	Investigator's Brochure
ID	Identification
ICF	Informed Consent Form
ICH	International Conference on Harmonisation of Technical Requirements for Registration of Pharmaceuticals for Human Use
ILI	Influenza-Like Illness
IM	Intramuscular
IRB	Institutional Review Board
IRT	Interactive Response Technology

MedDRA	Medical Dictionary for Regulatory Activities
MN	Microneutralization
NA	Neuraminidase
NOCD	New Onset of Chronic Disease
NP	Nasopharyngeal
NH	Northern Hemisphere
PCR	Polymerase Chain Reaction
PFS	Pre-filled Syringes
PP	Per Protocol
PPS	Per Protocol Set
PRO	Patient Reported Outcome
PV	Pharmacovigilance
PT	Pertussis Toxin
aQIV	Adjuvanted Quadrivalent Influenza Vaccine
QIV	Quadrivalent Influenza Vaccine
RT-PCR	Reverse Transcription Polymerase Chain Reaction
SAE	Serious Adverse Event
SAP	Statistical Analysis Plan
SC	Seroconversion
SDA	Source Data Agreement
SOC	System Organ Class
SOP	Standard Operating Procedure
TdaP	Tetanus Toxoid, Reduced Diphtheria Toxoid and Acellular Pertussis
TIV	Trivalent Influenza Vaccine
TNF	Tumor Necrosis Factor
VSAE	Vaccine Serious Adverse Events
WHO	World Health Organization

DEFINITIONS

Culture confirmed matched strains are defined by as those with a < 8 fold difference in titer as compared to the vaccine strain.

Culture confirmed unmatched strains are defined as those with a ≥ 8 fold difference in titer as compared to the vaccine strain.

End of influenza season: The end of the influenza season will be defined as the end of June for Northern Hemisphere (NH) influenza season and end of December for Southern Hemisphere (SH) influenza season. For tropical countries, with no typical NH or SH influenza season, the season is defined by the use of the strains in the vaccine formulation (i.e. strains as recommended for the NH or the SH influenza season) and the timing of vaccination.

Influenza case: An ILI associated with RT-PCR or culture confirmed influenza.

ILI onset: The first day on which a subject fulfils the criteria for protocol-defined ILI.

Medically-attended Adverse Event³: Defined as symptoms or illnesses requiring hospitalization, or emergency room visit, or visit to/by a health care provider.

Modified CDC Influenza-like illness (ILI)⁴: Fever (temperature of $> 37.2^{\circ}\text{C}/99^{\circ}\text{F}$) with cough or sore throat.

Protocol-defined ILI: At least one of the following respiratory symptoms: sore throat, cough, sputum production, wheezing, or difficulty breathing; concurrently with at least one of the following systemic symptoms: temperature of $> 37.2^{\circ}\text{C}/99^{\circ}\text{F}$, chills, tiredness, headache, or myalgia.

Qualified healthcare professional: Any licensed health care professional who is permitted by institutional policy to perform clinical interventions and assessments such as physical examinations and who is identified within the Study Staff Signature Log.

Trained healthcare professional: Any health care professional who is permitted by institutional policy and trained to perform delegated tasks and who is identified within the Study Staff Signature Log.

³ Please also refer to the CRF instructions for further guidance.

⁴ The respiratory symptoms in both definitions are considered a new onset or exacerbation of a pre-existing condition.

1. BACKGROUND AND RATIONALE

1.1 Background

Seasonal influenza is a major cause of morbidity and mortality in the elderly. On average from 1976 through 2007, nearly 90% of all deaths attributed to seasonal influenza in the United States occurred in people 65 years of age or older. During this period the number of deaths per year in the elderly population ranged from 673 to 5,546 per year (MMWR, 2010). Much of the mortality attributed to influenza is due to respiratory and cardiovascular illnesses, such as secondary bacterial pneumonia and exacerbation of underlying cardiac and respiratory disease (Mullooly, 2007).

Vaccination is an effective way to prevent influenza and the related complications. In the US seasonal influenza vaccination was estimated to prevent 3.2 million medically attended illnesses and nearly 80,000 fewer hospitalizations (MMWR, 2013). It is estimated that 56% of the prevented hospitalizations were amongst patients 65 year or older (MMWR, 2013). In an earlier study of elderly not residing in chronic care facilities, vaccination was associated with a 27% reduction in the risk of hospitalization for pneumonia or influenza and a 48% reduction in the risk of death (Nichol, 2007). Seasonal influenza vaccination also appears to have a salutary effect on the incidence of cardiac diseases. In a prospective randomized controlled study of patients with recent myocardial infarction, seasonal influenza vaccination reduced the incidence of subsequent cardiovascular death and re-hospitalization (Gurfinkel, 2002). Since the majority of influenza-related hospitalizations and deaths occur in the elderly, the derived benefit of vaccination in this age group is large. However, the effectiveness and efficacy of current influenza vaccines is substantially reduced in the elderly relative to younger populations (Osterholm, 2012; Beyer, 2013 and MMWR 2013). The reason for the reduced efficacy of influenza vaccines in the elderly is not completely known but may be explained by qualitative and quantitative differences in the immune response after vaccination (Goodwin, 2006; Sasaki 2011). The risk of complications from influenza infection is uniform amongst the elderly and chronic medical illness appears to increase the risk of hospitalization due to pneumonia and influenza and death. A clinical prediction rule was previously developed and validated to determine the risk of complications from influenza infection in the elderly (Hak, 2004).

Therefore, vaccines with improved effectiveness in the elderly could further reduce the burden of disease resulting from complications of influenza. One way to increase immunogenicity of influenza vaccines is through the use of adjuvants, such as the squalene and water emulsion, MF59. FLUAD[®], Seqirus' trivalent influenza vaccine combined with MF59, has been licensed for use in Europe since 1997. When administered to elderly, this vaccine results in significantly higher geometric mean HI titers and rates of seroconversion in comparison to a non-adjuvanted trivalent influenza

vaccine (TIV) ([Scheifele, 2013](#); [Frey et al. 2014](#)). The improved immunogenicity of FLUAD is not associated with significant increase in risk compared with non-adjuvanted vaccine. Administration of FLUAD to elderly patients results in higher local and systemic reactogenicity compared with non-adjuvanted vaccines but the reactions are mild and self-limited ([Scheifele, 2013](#); [Frey, 2014](#)). In a large prospective, observational study and a smaller, retrospective, case-control study, FLUAD appears to be more effective than non-adjuvanted comparators ([Mannino, 2012](#); [VanBuynder, 2013](#)). Furthermore, there does not appear to be an increased risk of rare but potentially serious adverse events based on a prospective analysis of subjects enroled in the study referred to above ([Villa, 2013](#)).

Seqirus has received accelerated approval by the United States Food and Drug Administration (FDA) to market FLUAD for the prevention of seasonal influenza in elderly subjects. Final licensure through the accelerated approval pathway is dependent on the demonstration of clinical benefit. Seqirus proposes to use a quadrivalent inactivated influenza vaccine combined with the adjuvant MF59, in this study and the FDA has agreed with this approach. Both aTIV and aQIV subunit vaccines are manufactured in a similar way and, in the case of aQIV, the fourth antigen is derived from a second B strain of influenza. B strains of influenza viruses are genetically classified into two main lineages, B/Yamagata and B/Victoria. During a typical influenza season, a single A/H1N1 and A/H3N2 will predominate. The epidemiology of disease caused by B strains is different and during the past decade it is common for both strains to circulate simultaneously ([Ambrose and Levin et al. 2012](#)). This can result in a clinically significant mismatch between the vaccine composition and circulating strains ([Lo, Chuang et al. 2013](#)).

The goal of this current randomized, observer-blind, controlled study is to demonstrate that aQIV prevents influenza in elderly adults. Direct comparison with a non-influenza comparator vaccine (Boostrix[®]) licensed for use in elderly adults, will enable an estimation of the absolute efficacy of aQIV in preventing influenza in elderly adults while simultaneously providing benefit to subjects randomized to not receive influenza vaccine. Placebos, or non-influenza vaccine comparators, have been used to show influenza vaccine efficacy in elderly subjects ([DeVilliers et al. 2009](#)). This approach is consistent with CBER Guidance for the licensure of seasonal influenza vaccines and was recently used to demonstrate the benefit of an inactivated non-adjuvanted quadrivalent vaccine in children ([Jain et al. 2013](#)).

The data from this study will be used to support the licensure of FLUAD and aQIV for the prevention of seasonal influenza in adults 65 years of age and older.

